Shade is the primary message, which embraces not only staying in the shade, but also staying out of the sun when the UVI reaches daily maximum (between 12 and 3 pm). The secondary message is *hat* and '*shade for the body*' meaning clothes. The tertiary message is *sunscreen*. The messages should be applied in combination to be effective.

The priority of the messages are in accordance with the European code against cancers suggestions for individual's protection against UVR. Avoidance of UVR by staying indoor in the middle of the day when UVR levels are highest obviously provides the best protection. Shade structures provide low protection against UVR (SPF = 2-5), due to reflection and diffuse UVR [12]. Textiles, like clothing and hats provides high protection of the covered areas (SPF > 50)[13], while hats only provide low protection on shaded areas, like the face (SPF 2-4)[14]. Sunscreens are produced with a theoretical SPF up to 50 in Denmark (requires distribution of 2 mg/ml) which is categorized as high. Consumers only apply approximately 0.5-1.0 mg/ml sunscreen, which means that the actual protection of sunscreens labeled with SPF 16 and SPF 36 drops below SPF 4 and SPF 6, respectively, which corresponds to low protection [15].

The campaign has achieved substantial successful results:

- The fraction of sunburn in the population in the Danish summer decreased from 44 % in 2008 to 22 % in 2014 [16]
- Use of sunbed decreased from 26 % in 2007 to 9 % in 2014 [17]

However:

- The fraction of sunburn in the population going on vacations to sunny destinations with high UVI was largely unchanged from 25 % in 2008 to 27 % in 2014 [18]

Vacations to sunny destinations is the most important arena for melanoma intervention

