A statistical power calculation shows that this sample size yields 95 % probability to detect a 10-percentage point drop from 50 % to 40 % in sunburn between an intervention group and the control group, and 80 % probability to detect a 7-percentage point drop from 50 % to 43 %. Our pilot study showed a 17-percentage point difference between our participants (32 %) relative to our annual sun surveys (49%). The number of invited participants to reach a final sample of ~2000 are included in the flow diagram in the protocol.

To obtain the final study sample size, we assumed 25 % of Danes invited to participate will volunteer for the project [41], >80 % will use of interventions (unpublished pilot study) and > 90 % will complete questionnaire [41, 42]. Loss to follow up after one year is expected to be 25 % according to travel patterns with high continuity of the Danes.

Multiple logistic regression analysis will be applied for analysis of differences in sunburn fraction. Analysis of variance will be used to analyze differences in sun protection score and UVR exposure score. Alpha criterion will be p=0.05 (two-tailed).

Intention-to-treat analysis will be applied by using multiple imputation by chained equations to account for missing information on sunburn among non-responders, using PROC MI in SAS 9.3. The imputation procedure includes variables hypothesized to potentially predict missing information (age, sex, education, skin type, sun behaviour, sun protection, sun intentions and intervention group). Analyses will be repeated including responders only and counting non-responders with same sunburn fraction as responders in the control group.

Clustering within families is not included in the planned analysis as it is unlikely to influence the results because participants from the same family have very low odds of being drawn with a total of 30.000 drawn out of the entire Danish population 18+ (app. 4.3 million).

Evaluation by validated questionnaire

Sun protective behavior, exposure to UVR and sunburn will be evaluated by use of a questionnaire validated by personal electronic UV-measurements [7, 43, 44]. This newly developed survey tool has made it possible in this project to evaluate the skin cancer interventions, without tracking of development of skin cancer which can take several years to develop after excessive UVR exposure. The short time period from intervention to evaluation minimizes recall bias.

Success criteria

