The primary success criteria of the effectiveness of the interventions is a 10 % decrease in sunburn fraction in the intervention groups as compared to the control group in the post-intervention measurement, as shown possible in the pilot study.

Furthermore, we aim to reach completion and response rates of no less than 90 % of the total sample, which we previously showed to be possible.

Secondary success criteria are increased awareness on the risk of skin cancer, increased use of protection (shade, clothes, hat and sunscreen) and decreased outdoor exposure when the UVI is highest between 12 and 3 pm. For all secondary success criteria, we aim for an improvement of 10 % between interventions and control group.

Potential bias

The randomization procedure ensures that all groups are similar; however, there is a risk of bias. The study population could be more or less likely to consist of sun seekers compared to the background population. This will not influence results of the trial because they should be equally distributed across the study arms. However, it could limit generalizability and influence future implementation of the interventions. The validated questionnaire allows us able to adjust for the received UV exposure of the participants in responder analyses.

Scientific and society perspectives and relevance

If the developed interventions are effective, they will be used in the Danish Sun Safety Campaign targeting Danes going on vacation to destinations with high UVI and thereby reduce the UVR exposure on a population level and eventually prevent skin cancers in Denmark. In addition, reductions in UVR exposure of the Danes will decrease the economic costs of skin cancer. The costs of skin cancer in Denmark were 250 million DKr annually during 2004-2008 [45]. While the return on investment (ROI) has not been estimated for Denmark, in Australia, the ROI for a campaign to prevent skin cancer was estimated to be 230 % [46].

Product and dissemination

The project will produce at least two scientific papers to document the effect of the study:

‘A randomized trial of Sun Safety Behavioral Interventions among Danes going to Sunny Destinations: Description and Baseline-study’

‘Sun Safety Behavioral Interventions among Danes going to Sunny Destinations: A Randomized Trial’

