majority of the elements in intervention 1. The feasibility of intervention 2 was previously shown [42, 61]. Ninety-three percent received and read the material. At posttest, we showed a sunburn rate in the study population, which was 17 percentage points lower than reported for our annual survey of the Danish population. All intervention elements (Sun advice, smartphone application, sunscreen application guide, skin type guide) proposed in this study were considered relevant and useful by more than 80 % of those who completed the pilot study. The skin type guide scored lowest with 81 % and the app scored highest with 95 % among those who had it available (google android and apple ios phones; not available for windows phones for instance). Furthermore, we saw a 9-percentage point increase in use of sunscreen, while use of long-sleeves and hat was largely unchanged. The hats proposed for the study, were not tested in the pilot, however the feasibility of the hat was previously tested in minor interventions. We also show a slight increase in knowledge of the UV Index in the population survey from 89 % to 93 % in the pilot test.

Potential pitfalls

Albeit highly unlikely, we have sketched various scenarios that could influence the project.

The project is based in the Danish Cancer Society, which means that during the project period, should any of the applicants change job, be long term absent/sick or likewise, qualified researchers of same level will replace them.

The project involves products from third part companies, which can be prone to internal or external structural changes or bankruptcy, leaving them no possibility to deliver a given product. In any case, an equally qualified product will be sought in replacement.

The recruitment method is register based. Should the Danish Civil Registry for some reason not be able to deliver data, like sudden legal changes in person data handling or likewise, other methods of recruitment are available.

All potential changes to the project will of course be reported to funder immediately.

Protocol

Time Schedule

Mar-Apr 2018	Planning of intervention & evaluation	Registering trial Ordering sample from civil registry system Preparation of interventions Preparation of information and homepage
Apr-May 2018	Recruitment and scheduling;	Sending invitations Ordering products for intervention Baseline Questionnaire

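### Does the unscaled 10 % in the primary success criterion leave effectiveness undefined?

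*Combined protocol and SAP*

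**What the plan says.** The Success criteria section states: "The primary success criteria of the effectiveness of the interventions is a 10 % decrease in sunburn fraction in the intervention groups", compared with control after the intervention, and adds that the pilot showed this to be possible. The sentence names no scale and no test. The secondary criteria use the same bare 10 %, worded as an aim.

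The section on statistical methods and power calculations is explicit about scale. It gives 95 % power for a "10-percentage point drop from 50 % to 40 % in sunburn between an intervention group and the control group". Its second design effect, with a stated power of 80 %, is also in points: 7, from 50 % down to 43 %. It names the analysis: "Multiple logistic regression analysis will be applied for analysis of differences in sunburn fraction". It sets alpha at 0.05, two-tailed. The Intervention study section hypothesises that the interventions will significantly reduce sunburn risk.

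The pilot is described twice, both times in points. The pilot summary gives a sunburn rate "which was 17 percentage points lower than reported for our annual survey of the Danish population", and the power section gives the two rates, 32 % and 49 %.

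**The concern.** A 10 % decrease in a proportion can mean one tenth of the control rate or ten points off it. From 50 %, these are drops to 45 % and to 40 %. The pilot does not separate them: 49 % against 32 % is 17 points, or 17/49 = 35 % relative, so it meets both.

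The sentence also leaves open whether success means a significant difference, an observed difference of the stated size, or both. The section on scientific and society perspectives says that effective interventions will go into the national campaign. A rule that can be read several ways could be settled after the results are known. On the relative reading, a 5-point observed drop could be called a success without being significant.

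**Working it through.** **Inputs.** There are 1,980 completers, two-tailed alpha 0.05 and a control rate of 50 % (power section). The allocation is in a flow diagram not available here, and the Intervention study section speaks of both three arms and four conditions. I therefore assume equal groups and show both cases: 1,980/4 = 495 and 1,980/3 = 660 per group. Paired results are in that order.

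**1. The plan's own figures.** With d the true drop, p̄ the mean of the two rates and n per group:

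Power = Φ[(d − 1.96·√(2p̄(1−p̄)/n)) / √((p₁(1−p₁)+p₂(1−p₂))/n)]

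- 50 to 40 %, n = 660: (0.10 − 1.96 × 0.02739)/0.02725 = 1.70, power 95.5 %. This reproduces the stated 95 %.
- 50 to 40 %, n = 495: (0.10 − 1.96 × 0.03162)/0.03146 = 1.21, power 88.7 %.
- 50 to 43 %: 59.8 % and 72.3 %. The stated 80 % is not reproduced two-sided (one-sided at 660 gives 81.8 %). That is a separate matter and does not affect the scale.

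**2. Which scale fits the design?** A 10-point criterion is the effect the plan powers for at 95 %. A relative criterion (50 to 45 %) would have power of 35 % and 44 %, below what the plan states for either of its design effects. Only the absolute reading makes the two sections agree.

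**3. What would be significant?** The smallest significant observed drop from 50 % solves d² = (1.96²/2n)(1 − d²), giving 6.2 and 5.4 points. An observed 5-point drop gives z = 1.575 and 1.819, p = 0.115 and 0.069. An observed 10-point drop gives p = 0.0016 and 0.0003. So at a 50 % control rate, an observed drop of at least 10 points is always significant. Requiring both conditions is then the same as requiring the observed drop, and only two distinct rules remain.

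**4. The two rules compared.** The chance that the observed drop reaches 10 points is 1 − Φ[(0.10 − d)/SE], where SE is the denominator in step 1.

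| True drop | Significant benefit | Observed drop ≥ 10 points |
|---|---|---|
| 0 | 2.5 % / 2.5 % (nominal) | 0.08 % / 0.01 % |
| 7 points | 60 % / 72 % | 17 % / 14 % |
| 10 points | 89 % / 96 % | 50 % / 50 % |
| 17 points (pilot) | not needed | 98.8 % / 99.6 % |

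Binomial simulation at a true 10-point drop gives 50 % and 51 % for the last column. In 39 % and 44 % of comparisons the result is then significant with an observed drop under 10 points.

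**The case for a change.** The authors knew the term percentage point and used it in the power section and the pilot summary, yet left it out of the one sentence that defines success. Even with the scale granted, the choice of rule moves the chance of success at a true 10-point effect from 89–96 % to about 50 %. The stated hypothesis carries no threshold and is not the success rule, so the plan offers two standards without ranking them. Logistic regression gives an odds ratio, which is on neither scale. For outcomes analysed as scores, a 10 % improvement has no defined unit.

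The textual omission stands, and so does the difference between the two rules. But a 50 % pass rate is what any threshold on the estimate gives when it is set at the true effect. It is not a flaw peculiar to this plan. Making significance alone decisive would let observed drops of about 5.4 to 6.2 points count as effective. That is below the only threshold the sponsor states, and the sponsor may have meant 10 points as the least effect worth putting into the campaign. The documents do not decide this, so a reviewer has no ground for preferring one rule. The odds ratio is no obstacle, because group sunburn fractions give the drop in points directly. The secondary criteria are worded as aims, and the plan does not say they are judged on the scores.

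**Conclusion.** No change to the plan follows. On scale, the bare 10 % is a clerical slip. The adjoining power statement and both accounts of the pilot point to 10 percentage points, and an analyst would read it that way. On the test, the hypothesis, model and alpha are all given, so following the plan yields a sound comparison of each intervention with control.

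What remains is a fair trade-off between two rules. Significance alone is more sensitive: 89 % or 96 % at a true 10-point drop. An observed 10-point threshold is stricter, at about 50 %, yet it would still pass an effect as large as the pilot's about 99 % of the time. Neither favours an ineffective intervention, which passes a single comparison with probability 2.5 % or less. Neither alters the sample size, the data collected or the primary analysis.

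These figures assume equal groups of 495 or 660, a 50 % control rate and an unadjusted comparison of two proportions. They are per comparison. Multiplicity across interventions, the number of arms and the unreproduced 80 % power are separate questions.

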Test of developed interventions to prevent skin cancer: a randomized study targeting Danes going on vacation to sunny destinations with high UV index

Date: July 21, 2018

Protocol ID: RCT429-2015-294

Test of developed interventions to prevent skin cancer: a randomized study targeting Danes going on vacation to sunny destinations with high UV index

Aim

The aim of the study is to test a series of developed effective interventions targeting Danes going on vacation to sunny destinations to decrease sunburn by increasing use of shade, hats, protective clothing, and sunscreen to prevent skin cancer in the Danish population.

Prevalence of skin cancer and sun exposure

Incidence of malignant and non-malignant skin cancer have increased for decades in large parts of the world and especially in Caucasian populations [1]. In Denmark, almost 4.000 individuals are diagnosed with a skin cancer annually (basal cell cancer not included) and more than 300 die from a skin cancer [2]. Exposure to ultraviolet radiation (UVR) from the sun and from artificial sources e.g. sunbeds is the main risk factor for skin cancer [3]. Sunburn is both a measure of the dose of UVR exposure received as well as an independent risk factor for skin cancer [4]. It has been estimated that up to 90 % of all skin cancers could be avoided by behavioral changes [5, 6]. One of the main sources of UVR exposure in the Danish population is vacations to destinations with high UV index (UVI) [7-11].

The Danish sun safety campaign

In 2007, the Danish Sun Safety Campaign was launched in a partnership between the Danish Cancer Society and the Danish foundation, TrygFonden. The purpose of the campaign is to prevent skin cancer in Denmark by increasing the use of appropriate sun protection in the natural sun and avoiding sunbed use in the Danish population. This study is going to be part of the Danish Sun Safety Campaign. Thus, experience from the campaign will be implemented in the study and study results will be used in the campaign afterwards.

The Danish Sun Safety Campaign's sun advice to prevent exposure to UVR from the natural sun are structured in three prioritized messages:

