To achieve the aim of this study we will conduct a randomized controlled trial with three arms during May-Dec 2017. Participants will be Danish adults traveling on vacation in 2018 for a period of 1-3 weeks, recruited from the civil registration system. After enrollment and pretesting, participants will be randomly assigned to one of three experimental conditions. Three experimental groups will receive innovative intervention strategies for promoting sun protection practices during vacation – Protection Routine (1), Protection Routine (2) or both Protection Routine (1+2). The fourth experimental condition will be a minimal treatment control group. The primary outcomes of the trial will be a reduction in frequency of sunburn by adherence to the current sun protection advice from the Danish Cancer Society, i.e., use of shade, hats, protective clothing, and sunscreen as secondary outcomes. We hypothesize that the following two interventions will be able to reduce significantly the UVR exposure and risk of sunburns in Danes going on vacation to destinations with high UVI.

Protection routine 1

The existing evidence of sun protection against the detrimental effect of UV radiation shows that it is effective if performed correctly [26, 28]. We will develop a package of existing training and information and test if it will lead to better adherence. The package will include:

- The rationale of the prioritized sun advice [32]
- Activity planner, with suggestions to why a break from the sun is beneficial and how to plan activities before and after UVI maximum i.e. morning/early noon and afternoon/evening [32]
- Download of the UV-application ‘UVindeks’ for smartphones developed by the campaign and activating UV alert of geographic destination [33]
- A skin type guide

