The preferred type of protection of the individual varies so the information and training package in this arm is intended to increase the overall protection level of the individual by advocating several sun protection practices. The sun advice is the most basal sun protection communication [32]. Moving outdoor activities away from UV peak hours will theoretical decrease the total UVR received, while maintaining constant outdoor activity level [32]. The smartphone application contains information on maximum UVI and cloud cover corrected UVI of any desired location in the world. The cloud cover corrected prognosis makes the information relevant to the recipient as oppose to the standard UVI-max prognosis provided by national weathercasts as these only change slightly through the season [34]. Using this intervention will provide participants with relevant information about sun protection at the right time in various geographic locations. In addition, a new alert to implement higher use of the sun advice ‘Shade’ is integrated in the application. The application also includes a skin

type test enabling specific messages about outdoor time before individual MED level is reached resulting in sunburn. This means users will receive an alert in the morning, if protection is needed, adapted to the location and UVR exposure to plan their time outdoors and avoid midday exposure. Dissemination of the UV Index alone has not shown to change peoples behavior [34]; however, it has been able to increase awareness [35], which is a precursor to changed behavior in behavioral models [36]. Additionally, sun safety smartphone applications have shown indications of improvement in sun protection practices in a randomized trial [37]. The skin type guide will also be provided as a paper version for individuals not using the smartphone application. Knowing your skin type is important. Several studies have shown that people overestimate their skin's thresholds for UVR exposure leading to sunburn [38]. This multi-faceted approach adapted to the individual should be able to show a behavioral improvement in sun exposure and protection.

Protection routine 2

Two of the largest pitfalls in Danes sun protection is 1) not covering the most skin cancer prone site on the body with a hat and 2) replacing clothing with insufficient amounts of sunscreen.

- A specially designed hat to wear in the sun to test the use of hat when it is available [39]

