- A newly developed instruction for correct application of sunscreen [40]

Denmark is not a hat-wearing society. By making smart design hats available and attractive may increase this sun protection behavior, which has large potential in prevention of skin cancer (**ibid: p2**). A very simple study showed that a brief instruction to sunscreen application increased the provided protection significantly [40].

Protection routine 1+2

The group will receive both above mentioned interventions and will reveal potential dose response effects from level of protection.

Control group

All groups including the control group will receive a minimal intervention with the current sun advice from the Danish Sun Safety Campaign.

Study population

The participants of the study are recruited from the Danish civil registration based system. The study population will represent all groups of the Danish population. Eligibility criteria for the project are persons living in Denmark going on vacation in May-December 2018 and having a smartphone compatible with either apple iOS (version 7.0 or newer) or Google Android (version 4.0 or newer). The period May to December is chosen as it includes all types of vacationers. The summer vacation constitutes the majority of the sunny vacations of the Danes. The period includes both the summer, where Danes typically travel to the Mediterranean area and the winter period where travel patterns change a bit to more exotic areas like Thailand, Egypt and the Canarias Islands. Exclusion criteria are persons younger than 18 years of age.

Randomization

The participants will be randomized to one of the intervention groups or to the minimal-treatment control group. The randomization procedure is described in the protocol.

Confounders

Possible confounders includes age, gender, education, skin type, skin cancer history, nevi, sun-seeking behavior and number of sunny vacations in past 5 years [28].

Statistical methods and power calculations

The number of completing participants (n= 1.980) is based on a power calculation, recruitment for similar studies conducted by the applicant [41, 42] and our recent pilot study (unpublished, summarized in the end of this application).

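### The plan leaves room to adjust responder analyses for received UV exposure, which the interventions aim to lower; a sunburn comparison adjusted this way would not estimate the total effect

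*Combined protocol and SAP*

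**What the plan says.** The sentence at issue closes the Potential bias section: "The validated questionnaire allows us able to adjust for the received UV exposure of the participants in responder analyses". It follows remarks that the sample may hold more or fewer sun seekers than the general population. The section says this should balance across arms and so leave the trial result alone, though it could limit generalisability.

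Other sections bear on that variable:

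- **Timing.** Under Intervention study: "After enrollment and pretesting, participants will be randomly assigned". Main study has the package arrive before departure. Under Evaluation by validated questionnaire and Data collection and handling, exposure and sunburn both come from a questionnaire sent after return.
- **Target of the interventions.** Under Intervention study: "We hypothesize that the following two interventions will be able to reduce significantly the UVR exposure and risk of sunburns". Protection routine 1 gives a mechanism: "Moving outdoor activities away from UV peak hours will theoretical decrease the total UVR received". No comparable statement about exposure is made for Protection routine 2, which is a hat and a sunscreen instruction.
- **Link to the primary outcome.** The background section on prevalence and sun exposure states: "Sunburn is both a measure of the dose of UVR exposure received".
- **Analysis.** Under Statistical methods and power calculations: "Multiple logistic regression analysis will be applied for analysis of differences in sunburn fraction", with no covariates named, and "Analysis of variance will be used to analyze differences in sun protection score and UVR exposure score". The same section plans an intention-to-treat analysis with multiple imputation and a repeat in responders only.
- **Confounders.** "Possible confounders includes age, gender, education, skin type, skin cancer history, nevi, sun-seeking behavior and number of sunny vacations in past 5 years". Received UV exposure is not on this list.

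**The concern.** The primary success criterion is a difference in sunburn fraction between intervention and control. That is a total effect: it counts every route by which an intervention prevents sunburn, including less UV received. Holding received exposure fixed takes that route out of the comparison.

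What remains is not cleanly a direct effect either. If exposure and sunburn share unmeasured causes, or exposure is reported with error, the adjusted coefficient mixes a direct effect with bias.

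The likeliest place for harm is the responder-only repeat. Its use is to show whether the handling of non-response drives the intention-to-treat result. If the repeat also adjusts for exposure, the two analyses target different quantities, and a gap between them could come from the adjustment alone.

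The plan gives no between-arm reason for adjusting. The worry stated just before the sentence is sun-seeking, a trait present before allocation, which the section itself expects to be balanced.

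**Working it through.** **Step 1: order of events.** Allocation and package come before departure. The vacation follows, and exposure and sunburn are reported after return. Received exposure is therefore a post-allocation variable. The plan hypothesises an effect of allocation on it and describes sunburn as a measure of it. On the plan's own account it can lie between intervention and sunburn.

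**Step 2: where the adjustment could enter.** The sentence refers to responder analyses, and the statistical section plans a repeat in responders. The logistic model has no stated covariates, so nothing rules the adjustment out. Nothing states that it will be used there either.

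**Step 3: illustration of size.** The plan gives no figure for this point, so there is none to reproduce. From the documents come only the 50% and 40% sunburn risks used for power: 40 - 50 = -10.0 points, odds ratio (0.40/0.60)/(0.50/0.50) = 0.667. Everything else is assumed:

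- X = mu·T + g·U + sqrt(1 - g²)·e, where T is allocation and U an unmeasured common cause; U and e are standard normal.
- logit P(sunburn) = a + b·X + h·U + c·T.
- a and the total shift d are solved so that the marginal risks are 50% and 40%. A share s of the effect runs through exposure: b·mu = s·d and c = (1 - s)·d.
- Reported exposure is X plus error, with reliability r.
- A logistic model is fitted on T and reported exposure, and the risk difference is standardised over pooled exposure.

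On the linear-predictor scale, E[U | T, X] = g·(X - mu·T), and the error shrinks the exposure slope by r. The coefficient of T becomes d·[1 - s·r·(1 + g·h/b)]. As a hand approximation for the risk difference:

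adjusted difference ≈ -10 × [1 - s·r·(1 + g·h/b)]

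With b = 0.7, h = 0.7 and g = +0.5, g·h/b = 0.5. For s = 0.5 and r = 1 this gives -10 × (1 - 0.5 × 1.5) = -2.5. With g = -0.5 and r = 0.5 it gives -10 × (1 - 0.5 × 0.5 × 0.5) = -8.75.

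Numerical integration of the full model gives, in percentage points (b = 0.7):

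| Scenario | s = 0 | s = 50% | s = 100% |
|---|---|---|---|
| No common cause, r = 1 (the true direct effect) | -10.0 | -5.0 | 0.0 |
| No common cause, r = 0.5 | -10.0 | -7.5 | -5.0 |
| Cause raises both (g = +0.5, h = 0.7), r = 1 | -10.0 | -2.5 | +4.9 |
| Same, r = 0.5 | -10.0 | -6.3 | -2.5 |
| Cause lowers exposure, raises sunburn (g = -0.5, h = 0.7), r = 1 | -10.0 | -7.5 | -5.0 |
| Same, r = 0.5 | -10.0 | -8.8 | -7.5 |

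The total effect is -10.0 throughout. A simulation of 2,000,000 records, run for five of the six half-mediated scenarios and for the fully mediated extreme of +4.9, agrees within 0.1 point. At s = 50% the range is -9.7 to -0.6 for b = 0.4 and -8.4 to -3.2 for b = 1.0.

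**Step 4: odds ratios.** With s = 0 the risk difference does not move, but the adjusted odds ratio falls between 0.59 and 0.67 over the slopes tried, against 0.667 unadjusted. That is non-collapsibility, not bias. It means that even without mediation an exposure-adjusted odds ratio need not match the main one.

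**The case against.** The strongest reply is that no planned analysis is shown to be wrong. The sentence describes what the questionnaire makes possible. A repeat of the analyses in responders most naturally means the same model in fewer people. Received exposure is absent from both the confounder list and the listed imputation variables. The surrounding text is about sun seekers and generalisability, and on that reading there is no estimand error. All of this stands. A reader might infer that the plan commits to an exposure-adjusted sunburn comparison; the text does not say so.

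Two further points also stand. The exposure mechanism is spelled out only for Routine 1. The content of the UVR exposure score is not given; if it reflects time outdoors rather than dose through protection, Routine 2 may hardly change it, and the risk difference would then hardly move. And post-vacation recording is not the right test for excluding a covariate. The Time Schedule plans to record UV Indexes for the destinations, and ambient UV at a destination chosen before allocation cannot be affected by it.

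The assumed parameters are open to challenge. Reliability 0.5 has no source in the documents, which call the questionnaire validated. Some candidate common causes, such as skin type, are on the confounder list, though whether they were collected before allocation is not stated.

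What remains is that the plan offers this adjustment as an answer to bias, does not say when it applies, and does not label the result as mediation.

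**Conclusion.** The point holds conditionally and is minor. If received exposure is adjusted for in a between-arm comparison of sunburn, that comparison does not estimate the total effect on which success is judged, and a responder repeat adjusted this way no longer isolates non-response. If the sentence is only about generalisability, nothing is wrong with the estimand.

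A reader might infer that the main result is biased. The documents do not support that: the adjustment is tied to responder analyses, and the intention-to-treat imputation analysis is not said to use it. A reader might also infer that the adjustment must hide a true effect. That does not follow. In the scenarios run, the adjusted difference moved from -10.0 towards zero or past it. But the hand formula shows that a common cause with g·h below -b would push it the other way, and with exposure unchanged by allocation the risk difference does not move.

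The figures show only that the distortion can range from none to large. They rest on assumed values of b, g, h, r and s; the 50% and 40% alone come from the plan.

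**What to change.** Replace the sentence under Potential bias with:

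> Between-arm comparisons of sunburn used to judge effectiveness, including the responder-only repeat, will not adjust for received UV exposure or any other variable that allocation could affect. The responder repeat will use the same model and covariates as the main analysis, for example baseline sun behaviour from sign-up. Any exposure-adjusted model will be reported separately as exploratory mediation with its assumptions stated.

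Name the covariates. Demographic items and baseline sun behaviour are taken at sign-up (Invitations). A baseline questionnaire is scheduled, but its contents are not given, so skin type, nevi, skin cancer history and past sunny vacations can be used only if they were collected before allocation. The destination's ambient UV Index need not be excluded if the destination was chosen before allocation. The plan should confirm this, because some people sign up before planning their trip.

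If the sentence was meant for generalisability, limit it to describing how participants compare with the background population.

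The cost is wording only, with no new data. The downside is that an exposure-adjusted estimate can no longer serve as supporting evidence of effectiveness.
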